7.7.2 Sensitivity Analyses

7.7.2.1 Multiple Imputation Assuming Missing at Random

This sensitivity analysis assumes that the diary data are missing at random (MAR), that is, the probability that an observation is missing may depend on the observed values but not the missing values (e.g., the probability of missing Week 5 diary is related to the observed Week 4 or Week 3 value but not the unobserved Week 5 value). In this sensitivity analysis, missing data is imputed multiple times, thus creating the multiply-imputed diary data. The final analysis incorporates the between-imputation variability with the within-imputation variability.

The SAS MI procedure is implemented using the following four steps.

1. Weekly IA total score is derived from the available Daily IA total scores (see Section 5.1). Weekly IA total score is set to missing if all Daily IA total scores are missing for the week.
2. SAS PROC MI is applied to the input dataset containing all weekly IA total scores during the baseline, titration, and maintenance period. The Markov Chain Monte Carlo (MCMC) method will be used for the multiple imputations. One hundred (100) multiply-imputed datasets will be created.
3. For each of the multiply-imputed data sets, PCH_T will be computed. The primary analysis based on the Wilcoxon rank-sum test will be conducted and the Hodges-Lehmann asymptotic 95% confidence intervals will be constructed.
4. To produce a single confidence interval for each dose and placebo comparison [REDACTED] mg versus placebo and [REDACTED] mg versus placebo), PROC MIANALYZE will be used and the Rubin's combination rules will be applied to the treatment effect estimates and associated asymptotic standard errors from the MI data sets. The treatment effect estimates will be defined as the midpoints of the asymptotic confidence intervals and the standard errors will be defined as the asymptotic standard errors (based on the width of the associated 95% confidence intervals) from the Hodges-Lehmann estimate of the individual datasets (Rubin 1987).

A sample SAS code is as follows.

```
PROC MI DATA=adqs NIMPUTE=100 SEED=123456789 MINIMUM=0 OUT=adqs_imp ;
  BY trtp ;
  VAR age sex bwk twk1 twk2 twk3 twk4 twk5 ;
  MCMC CHAIN=multiple IMPUTE=full INITIAL=em PRIOR=jeffreys ;
  RUN ;
```

where trtp is treatment group, bwk, twk1, twk2, twk3, twk4, and twk5 are variables of weekly IA scores during the baseline, and treatment (titration + maintenance) periods. These are derived as $(SUM/DAY)*7$, where SUM is the total of the IA scores reported on the IA diary in that analysis

week, and DAY is the number of days with non-missing IA score in the IA diary in that analysis week. Analysis week is defined as: 1st week is the 1st 7 days after visit 3 (exclusive) during titration, 2nd week is the rest of the days up to Visit 5 (inclusive) in titration period, 3rd week is the 1st 7 days after Visit 5 (exclusive), 4th week is the following 7 days after 3rd week, the 5th week is the rest of the days in maintenance period up to Visit 6 (inclusive). Adqs is the input data set with missing values, and adqs_imp is the complete imputed data set after 100 imputations. For the weekly IA score calculation, if the week has <3 daily diaries, the weekly IA score for this week will be set to missing and imputed using the above procedure.

From the above multiply-imputed IA data, the Hodges-Lehmann confidence interval will be calculated for each imputed data set. The point estimate for the between group difference and the associated standard error (SEM) will be derived from the confidence interval. These point estimates and the SEMs will be summarized by the SAS MIANALYZE procedure. A sample SAS code is as follows.

```
PROC MIANALYZE DATA=PARMEST ;
  MODELEFFECTS estim ;
  STDERR sem ;
  ODS OUTPUT PARAMETERESTIMATES=parmest2(KEEP= paramcd label estimate
                                             stderr lclmean uclmean probt) ;
  RUN ;
```

where estim and sem are the point estimate and SEM from each imputed set, estimate, stderr, lclmen, uclmean, and probt are the final summarized point estimate, standard error, lower and upper confidence limits, and the p-value for the between group comparison (Table 14.2.1.2.1).

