3.3.4 Blinding

Subjects, all site personnel, the Sponsor and its designated Contract Research Organizations (CROs) are blinded with the following exceptions. The CRO and Sponsor personnel who are

involved in the randomization generation, study drug supply, and PK concentration assays are unblinded. However, they are not involved in the routine study monitoring, data cleaning and review, the design of this SAP or data analysis.

3.4 *Hypotheses*

The null and alternative hypotheses are:

- H_{01} : There is no difference between SPN-810 █ mg and Placebo in the treatment of IA in subjects with ADHD in conjunction with standard ADHD treatment.
- H_{a1} : There is a difference between SPN-810 █ mg and Placebo in the treatment of IA in subjects with ADHD in conjunction with standard ADHD treatment.
- H_{02} : There is no difference between SPN-810 █ mg and Placebo in the treatment of IA in subjects with ADHD in conjunction with standard ADHD treatment.
- H_{a2} : There is a difference between SPN-810 █ mg and Placebo in the treatment of IA in subjects with ADHD in conjunction with standard ADHD treatment.

3.5 *Determination of Sample Size*

Based on results from the Phase 2 study, it is assumed that the average treatment difference between SPN-810 dose groups and placebo is 15 with a common standard deviation of 27.3 in the primary efficacy endpoint. A sample size of 77 subjects per arm (231 subjects for 3 arms) will yield 90% power to detect a non-zero difference between the median of active drug group █ mg or █ mg dose) and the placebo group using the Wilcoxon rank-sum test with a 2-sided significance level $\alpha=0.05$.

It is assumed that approximately 20% subjects will dropout before the completion of the study and hence, an adjusted total of 291 subjects will be randomized in a 1:1:1 ratio to obtain 231 subjects in the ITT population at the completion of the study.

To estimate the variability for designing Study 810P503, the standard deviation (SD) of the primary endpoint for Study 810P301 was reviewed blindly. This review indicates that the SD for interim data was actually 34.83 instead of the protocol-assumed 27.3 (see above). This increase in the SD resulted in the increase in the sample size to 122 subjects per treatment. Allowing for 20% dropout, the final sample size for randomization is 153 subjects per treatment.

The sample size was calculated using the nQuery Advisor Software, Version 7.

3.6 *Changes to Analyses Planned in the Protocol*

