5 EFFICACY AND SAFETY VARIABLES

5.1 Primary Efficacy Variable

The primary efficacy endpoint is percent change (PCH_T) in the frequency (unweighted score) of IA behaviors per 7 days in the treatment (titration and maintenance) period relative to the Baseline period calculated over the number of days with non-missing IA diary data.

PCH_T will be calculated as $100 \times (T - B)/B$, where T and B are IA behavior frequencies per 7 days during the treatment period (from Day 2 through Visit 6, inclusive) and baseline period (Day ≤ 1), respectively. The IA behavior frequency per 7 days is defined as $(SUM/DAY) \times 7$, where SUM is the total of the IA behaviors reported in the subject IA diary, and DAY is the number of days with non-missing IA score in the subject IA diary during the specified study period.

This primary efficacy variable will be based on a checklist of 15 IA behaviors collected in an electronic IA diary. The IA diary comprises two parts: 1) An episodic diary that will be used by the primary caregiver (or alternate) to enter events as soon as possible after they are observed; and 2) an evening diary that will prompt the caregiver to review events for the day and to enter any events that were not previously captured. Each event will be characterized by a checklist of 15 observed behaviors: Yelling, Screaming, Threatening, Scratching, Throwing, Slamming, Hitting Self, Arguing, Cursing, Name Calling, Shoving, Hair Pulling, Fighting, Hitting Others, and Kicking Others. The checklist will indicate whether each behavior was observed (coded 1) or was not observed (coded 0) during the incidence of an event. Each day can have multiple events. A day can have no event, as can be attested in the evening diary. In this case, if no event is reported during a day, and the evening diary confirms this, the daily event score for that subject will be 0 for each of the 15 IA variables. Behaviors not on this list will not be captured.

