6.4 Handling of Dropouts, Missing Data, and Data Discrepancies

For the primary analysis of the primary efficacy endpoint, the frequency of IA behaviors during the treatment (titration + maintenance) period will be calculated over the number of days with non-missing IA diary data in the treatment period. No explicit imputation of missing data will be used, but this approach is implicitly equivalent to using the frequency of IA behaviors during the days with non-missing IA diary data to impute the frequency for days after study discontinuation or days with missing IA diary data. In addition to this implicit imputation, multiple imputations under the assumption of missing at random (MAR) and missing not at random (MNAR) will be used for handling missing data for sensitivity analysis. Details of imputation methods are specified in Section [7.7.2](#).

For analysis of frequency of IA behaviors during the treatment period (titration or maintenance), the following methods will be followed.

- 1) If subjects discontinued the study during the maintenance period, their maintenance period will be counted from Visit 5 (exclusive) through the date of last dose as documented on the End of Study eCRF page (inclusive). If the date of last dose is not collected, it will be imputed by the subjects' last visit for the study.
- 2) If subjects have ≥ 7 daily diaries in the maintenance period, their maintenance IA frequencies will be based on maintenance daily diaries.
- 3) If subjects have <7 daily diaries in the maintenance period, their maintenance IA frequencies will be calculated pooling the titration period diaries with the maintenance period diaries.
- 4) If subjects do not have any maintenance diaries, their maintenance IA frequencies will be entirely derived from the titration period diaries.

Missing data for secondary efficacy endpoints will be handled by using the Mixed Model for Repeated Measures method, which is implemented via SAS® PROC MIXED procedure. MMRM assumes data are “Missing At Random (MAR)”. That is, the probability that an observation is missing may depend on the observed values but not the missing values in the previously scheduled visits.

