7.7.2.2 Multiple Imputation Assuming Missing Not at Random

This sensitivity analysis assumes that the diary data are missing not at random (MNAR), that is, the probability that an observation is missing may depend on its underlying unobserved value.

This approach may be considered “worst-case” sensitivity analyses as it assumes that after discontinuation subjects from the dosing arms would adopt the outcome model estimated from the placebo arm. To generate missing values from this “placebo-based” imputation model, PROC MI with the MNAR statement will be used (Table 14.2.1.2.2). A sample SAS code is as follows.

```
PROC MI DATA=adqs NIMPUTE=100 SEED=123456789 MINIMUM=0 OUT=adqs_imp ;
  CLASS trtp ;
  VAR age sex bwk twk1 twk2 twk3 twk4 twk5;
  FCS reg ;
  MNAR MODEL(bwk twk1 twk2 twk3 twk4 twk5 / MODELOBS=(trtp='Placebo')) ;
  RUN ;
```

where multivariate imputation is carried out by the fully conditional specification (fcs) method.

7.7.3 *Analysis of PCH Based on Data from Maintenance Period*

For this sensitivity analysis, the primary analysis will be repeated using data restricted to the maintenance period only (Table 14.2.1.2.3).

7.7.4 *Supplementary Analysis*

A supplementary analysis will be performed based on the Per Protocol population and will be presented in Table 14.2.1.2.4.

7.7.5 *Analysis Based on Adjustment of Covariates*

An exploratory analysis of the primary efficacy endpoint will be performed using a randomization-based approach (Dmitrienko and Koch 2017). Separate models will be produced for the following key prognostic baseline characteristics (age [categorical and continuous] and gender [categorical]) will be used in this analysis. In addition, pooled site and baseline IA adjusted to 7 days will be used as covariates (Table 14.2.1.4).

7.7.6 *Examination of Subgroups*

The primary and key secondary efficacy (Caregiver CGI-I and Investigator CGI-I) variables will be summarized by subgroup to explore the heterogeneity of the treatment effect across subgroups. This analysis will be done for the following subgroups: gender (male, female), age (6-9 and 10-12), and race (White, Black/African American, Other) (Table 14.2.1.5a - Table 14.2.1.5c).

7.7.7 *Secondary Efficacy Analyses*

All secondary analyses are based on the ITT population to compare the █ mg dose with the Placebo. The secondary analysis variables are:

1. Actual Caregiver CGI-I score at Visits 4, 5, and 6 (Table 14.2.2 and Listing 16.2.2.2)

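### Imputing raw weekly IA scores with a normal model and a floor at zero raises the imputed values, and can distort both multiple-imputation sensitivity analyses when dropout differs by arm

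*SAP*

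**What the plan says.** SAP 7.7.2.1 (missing at random) gives sample code that calls "PROC MI DATA=adqs NIMPUTE=100 SEED=123456789 MINIMUM=0 OUT=adqs_imp" with "MCMC CHAIN=multiple IMPUTE=full INITIAL=em PRIOR=jeffreys", run separately by arm on "VAR age sex bwk twk1 twk2 twk3 twk4 twk5". The MCMC method is a joint multivariate normal model. SAP 7.7.2.2 (missing not at random) repeats the same procedure line, uses linear regression under fully conditional specification (FCS), and takes its model from placebo: "MNAR MODEL(bwk twk1 twk2 twk3 twk4 twk5 / MODELOBS=(trtp='Placebo". Neither block has a transformation, predictive mean matching or a count model.

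The imputed variables are weekly rates, built from a sum over diary days ("where SUM is the total of the IA scores reported on the IA diary in that analysis" week) divided by the days observed and multiplied by 7. They cannot be negative, and zero is possible: under SAP 5.1, on a confirmed event-free day, "the daily event score for that subject will be 0 for each of the 15 IA variables".

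Both analyses are sensitivity analyses. For the primary analysis, SAP 6.4 states: "No explicit imputation of missing data will be used". SAP 3.5 plans for dropout without splitting it by arm ("It is assumed that approximately 20% subjects will dropout before the completion of the study") and reports a blinded SD of 34.83 for the primary endpoint.

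**The concern.** A normal model fitted to a score bounded at zero produces some negative draws whenever its predictive SD is sizeable relative to its mean. The bound rejects these, so the accepted values come from a truncated normal whose mean lies above that of the fitted model. The relative rise is largest where predicted scores are low, and the endpoint is a percent change.

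These two analyses are the plan's main evidence on whether the primary result depends on missing diaries, and protocol 6.9.3 regards such checks as crucial when dropout is high. If truncation moves the treatment difference, the missing-at-random result is not purely a consequence of that assumption. In the placebo-based analysis, which SAP 7.7.2.2 presents as a worst case, a reader could not separate the effect of the assumption from that of the floor.

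**Working it through.** The plan states no figure on this point, so there is none to reproduce.

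**1. Direction.** A normal(m, s) variable redrawn until it is at least 0 has its mean raised by s·φ(m/s)/Φ(m/s). As a fraction of m:

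| s/m | Share below 0 | Rise in mean |
|---|---|---|
| 0.3 | 0.04% | 0.0% |
| 0.5 | 2.3% | 0.5 × 0.0540/0.9772 = 2.8% |
| 0.75 | 9.1% | 13.5% |
| 1.0 | 15.9% | 1.0 × 0.2420/0.8413 = 28.8% |

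Redrawing is the standard meaning of the option; the SAP does not describe it. The direction does not depend on it. Setting negative draws to 0 gives a mean of m·Φ(m/s) + s·φ(m/s), which at s/m = 1 is 0.8413 + 0.2420 = 1.083 times m, a rise of about 8%.

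**2. Size, by simulation.** From the SAP: 122 per arm, about 20% dropout, percent-change SD near 34.83 (all 3.5), and a baseline score plus five weekly scores (7.7.2.1). Assumed: Poisson-lognormal weekly scores, baseline mean 40 per week, between-subject coefficient of variation (CV) 0.5 to 1.2, monotone dropout at random, and an unequal split of about 10% placebo v 31% active. Each scenario used 120 trials with 8 imputations, by sequential Bayesian normal regression, which is equivalent to normal-model imputation for monotone dropout.

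The shift is the Hodges-Lehmann difference (active minus placebo) with the floor, minus a reference. The reference is the complete-data difference for missing at random (MAR), and the log-scale placebo-based difference for missing not at random (MNAR). A positive shift is toward no effect.

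| CV; dropout placebo/active | Placebo SD | Redrawn | Imputed v true score, placebo; active | MAR shift | MNAR shift |
|---|---|---|---|---|---|
| 0.8; 20%/19% | 32.8 | 6.4% | +6.0%; +6.7% | −11.16 − (−11.02) = −0.14 | −10.49 − (−10.47) = −0.02 |
| 1.2; 20%/19% | 35.6 | 10.1% | +13.7%; +10.5% | −12.28 − (−11.85) = −0.43 | −11.44 − (−11.08) = −0.36 |
| 0.5; 10%/31% | 31.5 | 3.3% | +1.4%; +2.4% | −11.08 − (−11.35) = +0.27 | −9.80 − (−10.18) = +0.38 |
| 0.8; 10%/31% | 32.6 | 6.2% | +6.3%; +6.6% | −10.75 − (−11.62) = +0.87 | −9.50 − (−10.36) = +0.86 |
| 1.2; 10%/31% | 35.9 | 9.9% | +12.1%; +12.7% | −9.70 − (−11.19) = +1.49 | −8.31 − (−9.96) = +1.65 |

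The Monte Carlo standard error of the MAR shifts is 0.07 to 0.12. The sampling SD of the difference itself is 3.1 to 3.5.

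A second Poisson-lognormal simulation had a percent-change SD of about 38 to 41, somewhat above the SAP's. It gave 8 to 12% of draws below zero and imputed scores 11 to 21% too high. The shift was at most about 0.6 points with equal dropout, 0.7 to 1.5 points toward no effect when active lost more, and 1.2 to 2.1 points in favour of active when placebo lost more.

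**3. Scale.** A 2-point shift is 2/11.51 = 17% of the difference assumed in protocol 6.10, or 2/15 = 13% of the first one in SAP 3.5.

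**4. Alternatives.** In the first simulation, log-scale imputation (offset 0.5) kept the MAR difference within about 0.4 points of complete data in every scenario. Removing the bound but keeping the normal model kept it within about 0.5. In the second simulation, either change brought the difference within about 0.3.

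**The case against.** The strongest reply is that a rise in imputed scores is not a bias in the comparison. Both arms rise together, and with similar dropout the net shift is small against a sampling SD above 3 points. That stands. An unequal split is hypothetical, because the documents give dropout only overall.

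It also stands that skewness is assumed. No mean, SD or shape is given for weekly scores. Entry requires R-MOAS of at least 24 and at least moderate CGI-S (protocol 4.1.1), and each event can score up to 15 behaviours, so weekly totals could sit well above zero. At s/m = 0.3 the floor does almost nothing. The rank-based test is only indirect evidence of skew.

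The code is labelled as a sample, and SAP 6.1 allows other methods before unblinding if assumptions fail. That makes the change easy but does not make it. The log-scale remedy is also favoured by lognormal simulated data. Removing the bound alone did about as well on the treatment difference, though it leaves impossible negative weekly scores.

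A reader might infer that both checks are simply biased, that every dropout's imputed weeks are too high, or that the primary result is compromised. The documents support none of these. The rise is an average one, it needs appreciable predictive mass below zero, and the primary analysis does not use these imputations. Shifts of 4 to 5 points did appear in simulation, but only with unequal dropout and a percent-change SD of about 74 to 77, roughly twice the SAP's 34.83.

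**Conclusion.** The point holds in a limited form. The mechanism follows from the code and the arithmetic above, and confidence in it is high. Confidence in the size is moderate, because it rests on assumed right-skewed weekly scores and assumed dropout splits. Where dropout is similar across arms, the two sensitivity results would be little changed. Where it differs, a shift of about 0.3 to 2 points could blur their reading. The direction that flatters the drug arises when placebo loses more children. This is a cheap improvement to two sensitivity analyses, not a threat to the trial's main conclusion.

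**What to change.** In both code blocks, remove MINIMUM=0 from the raw-scale normal model and impute log(weekly score + 1) for the baseline and five treatment weeks. Back-transform, and set any value below 0 to 0 before computing PCH_T. The floor is still needed because a log-scale draw below 0 back-transforms to exp(z) − 1, between −1 and 0; it then alters a weekly score by less than one behaviour.

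Alternatively, use predictive mean matching. For the missing-at-random analysis, that means changing the stated MCMC step to FCS.

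Keep the variables, the 100 imputations and the combining rules. The cost is a small change to code and SAP text. It should be made before unblinding, so that the choice of imputation model cannot look driven by results.

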7.7.2.2 Multiple Imputation Assuming Missing Not at Random

This sensitivity analysis assumes that the diary data are missing not at random (MNAR), that is, the probability that an observation is missing may depend on its underlying unobserved value.

This approach may be considered “worst-case” sensitivity analyses as it assumes that after discontinuation subjects from the dosing arms would adopt the outcome model estimated from the placebo arm. To generate missing values from this “placebo-based” imputation model, PROC MI with the MNAR statement will be used (Table 14.2.1.2.2). A sample SAS code is as follows.

```
PROC MI DATA=adqs NIMPUTE=100 SEED=123456789 MINIMUM=0 OUT=adqs_imp ;
  CLASS trtp ;
  VAR age sex bwk twk1 twk2 twk3 twk4 twk5;
  FCS reg ;
  MNAR MODEL(bwk twk1 twk2 twk3 twk4 twk5 / MODELOBS=(trtp='Placebo')) ;
  RUN ;
```

where multivariate imputation is carried out by the fully conditional specification (fcs) method.

7.7.3 *Analysis of PCH Based on Data from Maintenance Period*

For this sensitivity analysis, the primary analysis will be repeated using data restricted to the maintenance period only (Table 14.2.1.2.3).

7.7.4 *Supplementary Analysis*

A supplementary analysis will be performed based on the Per Protocol population and will be presented in Table 14.2.1.2.4.

7.7.5 *Analysis Based on Adjustment of Covariates*

An exploratory analysis of the primary efficacy endpoint will be performed using a randomization-based approach (Dmitrienko and Koch 2017). Separate models will be produced for the following key prognostic baseline characteristics (age [categorical and continuous] and gender [categorical]) will be used in this analysis. In addition, pooled site and baseline IA adjusted to 7 days will be used as covariates (Table 14.2.1.4).

7.7.6 *Examination of Subgroups*

The primary and key secondary efficacy (Caregiver CGI-I and Investigator CGI-I) variables will be summarized by subgroup to explore the heterogeneity of the treatment effect across subgroups. This analysis will be done for the following subgroups: gender (male, female), age (6-9 and 10-12), and race (White, Black/African American, Other) (Table 14.2.1.5a - Table 14.2.1.5c).

7.7.7 *Secondary Efficacy Analyses*

All secondary analyses are based on the ITT population to compare the █ mg dose with the Placebo. The secondary analysis variables are:

1. Actual Caregiver CGI-I score at Visits 4, 5, and 6 (Table 14.2.2 and Listing 16.2.2.2)
2. Actual Investigator CGI-I score at Visits 4, 5, and 6 (Table 14.2.3 and Listing 16.2.2.2)
3. Change from baseline (Visit 3) to Visits 4, 5 and 6 in Investigator CGI-S (Table 14.2.4 and Listing 16.2.2.3)
4. CHQ-PF28 Aggregate Physical and Psychological Scores will be summarized at Visit 6 (Table 14.2.5 and Listing 16.2.2.4a – Listing 16.2.2.4c)
5. PSI-4-SF will be summarized at Visit 6 (Table 14.2.6, Listing 16.2.2.5a, and 16.2.2.5b)
 - a. Parental Distress
 - b. Parent-Child Dysfunctional Interaction

- c. Difficult Child
- 6. SNAP-IV ADHD scores will be summarized at Visit 6 in (Listing 16.2.2.6a and Listing 16.2.2.6b):
 - a. Inattention ratings (Table 14.2.7.1)
 - b. Hyperactivity/Impulsivity ratings (Table 14.2.7.2)
 - c. Oppositional Defiant Disorder (Table 14.2.7.3)
 - d. Combined Scale ratings (Table 14.2.7.4)

Scores of CGI-I and CGI-S will be analyzed using a Mixed-Effects Model for Repeated Measure (MMRM). The model includes treatment, visit, and interaction between treatment and visit as fixed factors, baseline CGI-S as covariate for both CGI-I and CGI-S. The model parameters will be estimated using restricted maximum likelihood method with unstructured variance-covariance matrix and Kenward-Roger approximation to estimate denominator degrees of freedom. In case there is a convergence problem in the MMRM model with the unstructured variance covariance matrix, the first (co)variance structure which does not have convergence problem will be used for the analysis from the following ordered list: 1) Toeplitz 2) Autoregressive of order 1 3) Compound symmetry. The least squares mean of each treatment group, the difference in the least squares mean (█ mg dose minus placebo and █ mg dose minus placebo), and the 2-sided 95% CI for the difference will be obtained.

A sample SAS code is provided as follows.

```
PROC MIXED DATA=XXXX ;  
  CLASS trtp(ref="P") usubjid visit;  
  MODEL Response = base trtp visit trtp*visit / DDFM=kr ;  
  REPEATED visit / SUBJECT=usubjid(trtp) TYPE=UN ;  
  Lsmeans trtp*visit/Pdiff alpha=0.05;"  
RUN ;
```

Note: usubjid is subject ID, trtp ("P" denotes placebo treatment) is treatment variable, visit is the nominal study visit, and Response is respective endpoints.

Scores for CHQ-PF28, PSI-4-SF, and SNAP-IV will be analyzed using analysis of variance (ANOVA) at Visit 6.

To preserve the overall type I error rate at 0.05 for the secondary endpoints, a sequential testing procedure will be used with the following features. First only dose or doses that are significantly different from placebo for the primary endpoint will be tested for secondary endpoints. If the primary endpoint analysis indicates only one dose is significant, no multiplicity adjustment is required. Otherwise, multiplicity adjustment will be performed as in the following. The first of the secondary endpoints will be compared to placebo using the Hochberg step up procedure but only using those doses retained as a result of testing the primary endpoint. The second secondary endpoint will be tested in the same manner but only using those doses that were retained from the primary and the first secondary endpoint and so forth. As the endpoints are gone through in

the pre-defined order doses will only be retained if significant for all endpoints tested so far and at the given stage the Hochberg step-up procedure will be applied.

If the null hypothesis for the primary analysis is not rejected, then no multiplicity adjustment will be done for the secondary endpoints. Otherwise, a sequential testing procedure to preserve the type I error rate at 0.05 will be conducted as described below.

The ordering of the secondary endpoints follows the order in the list above.

